#### 4.7 STUDY DISCONTINUATION

This study may be terminated by Cole Eye Institute/Cleveland Clinic or Genentech at any time. Reasons for terminating the study may include the following:

- The incidence or severity of adverse events in this or other studies indicates a potential health hazard to subjects
- Subject enrollment is unsatisfactory
- Data recording is inaccurate or incomplete

#### 4.8 STATISTICAL METHODS

#### 4.8.1 Analysis of the Conduct of the Study

There is no formal sample size calculation in a pilot study. As this is a pilot study, a sample size of **30** patients is chosen, making sure that it is feasible to conduct the study and logistically to complete the study within **2** years.

If and when the study is planned for a phase II/III randomized control trial, appropriate statistical analysis will be determined.

# 4.8.2 Safety Analyses

Any adverse events, laboratory assessments, physical examinations, vital signs, ocular examinations and measurements from all **30** subjects will be utilized to summarize safety data for this pilot study.

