#### 2.1 Primary Objective

The primary objective of the study is to assess the ocular and systemic adverse events of ranibizumab for DME following previous treatment with intravitreal bevacizumab (worsened acuity >30 letters, retinal detachment, endophthalmitis, cataract progression, vitreous hemorrhage, new PDR or neovascularization of the iris or angle, systemic thromboembolic events, deaths and systemic serious adverse events).

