# 3. STUDY DESIGN

# 3.1 DESCRIPTION OF THE STUDY

This is an open-label, Phase I/II study of intravitreally administered 0.3mg ranibizumab in subjects with DME previously treated with intravitreal bevacizumab with a randomized comparative dosing strategy (monthly vs "treat-and-extend"). Thirty patients total will be enrolled in the study, 15 in each group. This study will have a 1-year treatment period. The recruitment period will occur over 1 year with a total potential study duration of 2 years. Interim analysis performed at 6 months and final analysis at 1 year.

Group 1 (monthly group) n=15

Consented, enrolled subjects will receive multiple open-label intravitreal injections of 0.3 mg ranibizumab administered every 30 days (+/- 7 days from the last treatment) for 12 months in the monthly group.

Group 2 ("treat-and-extend" group) n=15

 In the "treat-and-extend" group, eyes will be treated with 3 loading doses at 30-day intervals (+/- 7 days from the last treatment). After the third loading dose, the follow-up interval is determined with an OCT-based protocol.

Angiography assessment:

Both qualititative and quantitative assessment of angiographic features will be performed on obtained angiograms. This will include evaluation of leakage, microaneurysms and ischemia. This is detailed in Appendix D. Addendum for

Prior anti-VEGF response assessment:

Utilizing available clinical and imaging data contained in the medical record, assessment of functional (visual acuity) and anatomic (OCT) responses will be assessed. This information would be assessed in detail following review of this data for appropriate inclusion/exclusion parameters for the study. This is detailed in Appendix E.

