# 4.1.2 Inclusion Criteria

Subjects will be eligible if the following criteria are met:

- Ability to provide written informed consent and comply with study assessments for the full duration of the study
- Age > 18 years
- ETDRS best-corrected visual acuity of 20/25 to 20/320 in the study eye
- Willing, committed, and able to return for ALL clinic visits and complete all study related procedures
- At least 6 previous bevacizumab injections for diabetic macular edema in the last 12 months.
- At least 2 bevacizumab injections within 10 weeks and the most recent bevacizumab injection within 6 weeks of baseline study visits
- Persistent foveal-involving diabetic macular edema based on presence of intraretinal and/or subretinal fluid by SDOCT in the foveal center at study entry

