#### 4.1.3 Exclusion Criteria

Subjects who meet any of the following criteria will be excluded from this study:

- Pregnancy (positive pregnancy test) or lactation
- Premenopausal women not using adequate contraception. The following are considered effective means of contraception: surgical sterilization or use of oral contraceptives, barrier contraception with either a condom or diaphragm in conjunction with spermicidal gel, an IUD, or contraceptive hormone implant or patch.

- Intravitreal steroid or periocular steroid treatment within 3 months of study entry
- Focal/grid laser photocoagulation treatment within 3 months of study entry
- Panretinal photocoagulation treatment within 3 months of study entry
- Prior vitrectomy in the study eye
- History of retinal detachment in the study eye
- Prior trabeculectomy or other filtration surgery in the study eye
- Active intraocular inflammation in either eye
- Active ocular or periocular infection in either eye
- Active scleritis or epicscleritis in either eye
- History of any other retinal vascular disease (e.g., retinal vein occlusion, retinal artery occlusion)
- Coexistent retinal disease other than diabetic retinopathy (e.g., AMD, inherited retinal disease)
- Intraocular surgery within 3 months of study entry.
- History of corneal transplant or corneal dystrophy
- Significant media opacities in study eye which may interfere with visual acuity
- Participation as a subject in any clinical study within 3 months of study entry.
- History of allergy to topical iodine
- Any other condition that the investigator believes would pose a significant hazard to the subject if the investigational therapy were initiated
- Participation in another simultaneous medical investigation or trial

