# Appendix D: Quantitative Assessment of Ultra-widefield Angiographic Features in Diabetic Macular Edema Addendum

Examples of quantitative segmentation of leakage and ischemia in ultra-widefield angiography. Quality permitting, UWFA obtained during study will be assessed for quantitative changes.

Figure 1: Diabetic macular edema and proliferative diabetic retinopathy with automated identification of retinal vascular leakage (green). Longitudinal assessment following anti-VEGF treatment. Areas of segmentation (e.g., green) able to be quantified in absolute or relative fashions for area.

Figure 2: Diabetic macular edema and proliferative diabetic retinopathy with automated identification of neovascular leakage (yellow), ischemia (blue) and retinal vascular leakage (green). Longitudinal assessment following anti-VEGF treatment. Areas of segmentation (e.g., green, yellow, blue) able to be quantified in absolute or relative fashions for area.

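### No at-risk denominator or unit of analysis is set for cataract progression, new PDR and loss of more than 30 letters, although eligibility admits study eyes that cannot show these events

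*Protocol*

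**What the plan says.** Section 2.1 of the protocol lists the events of the primary objective, among them "worsened acuity >30 letters, retinal detachment, endophthalmitis, cataract progression, vitreous hemorrhage, new PDR or neovascularization of the iris or angle". Sections 3.3.1 and 4.8.2a define the primary endpoint more broadly, as the incidence and severity of ocular and of non-ocular adverse events.

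The only statement on whose data enter the safety summary is in section 4.8.2: "ocular examinations and measurements from all 30 subjects will be utilized to summarize safety data for this pilot study". Section 3.1 fixes the numbers: "Thirty patients total will be enrolled in the study, 15 in each group". The SAP adds a chi-squared comparison of ophthalmic adverse event frequency at the 0.05 level. Neither document names a denominator for a particular event, or says whether ocular events are counted per study eye, per treated eye or per subject.

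The entry criteria that bear on this are:

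- **Lens status.** Section 4.1.3 excludes intraocular surgery only within 3 months of entry. An eye made pseudophakic by earlier surgery can enter.
- **PDR.** Section 4.1.3 lists "Panretinal photocoagulation treatment within 3 months of study entry" as an exclusion, but not PDR itself. Its exclusion for coexistent retinal disease exempts diabetic retinopathy without a severity limit.
- **Acuity.** Section 4.1.2 requires "ETDRS best-corrected visual acuity of 20/25 to 20/320 in the study eye".

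Section 4.1.1 allows fellow eyes with DME to receive ranibizumab at the investigator's discretion. Section 4.2 mentions no stratification of the randomisation.

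**The concern.** Some eligible study eyes cannot show some of the named events. A pseudophakic eye cannot have cataract progression. An eye with PDR at entry cannot develop PDR anew. An eye that enters with 30 letters or fewer cannot lose more than 30. If these eyes stay in the denominator, the rate for that component comes out too low, and a count of zero looks more reassuring than it is.

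A second effect concerns the arms. With 15 subjects per group and no stratification, the number of eyes at risk can differ between arms by chance. A comparison over 15 and 15 then partly reflects lens or PDR status at entry instead of the dosing regimen.

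**Working it through.** **Inputs from the documents.** N = 30, 15 per arm (section 3.1); 15 + 15 = 30 agrees. N rests on feasibility (section 4.8.1: "There is no formal sample size calculation in a pilot study"), so there is no power figure to reproduce. The lowest admitted acuity is 20/320 (section 4.1.2).

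**Assumptions, not in the documents.** The share of eyes not at risk, taken as 20%, 40% and 60% for lens status. An illustrative count of 5 cataract events. A letter scale with 85 letters at 20/20 and 5 letters per 0.1 logMAR.

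**1. Dilution.** With x events and r eyes at risk, the all-subject rate is x/30 and the at-risk rate is x/r. Their ratio is (x/30)/(x/r) = r/30, whatever x is.

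**2. Five events.** The all-subject rate is 5/30 = 16.7% (exact 95% interval 5.6% to 34.7%).

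| Assumed pseudophakic | Phakic r | r/30 | 5/r | Exact 95% interval |
|---|---|---|---|---|
| 20% | 24 | 0.80 | 20.8% | 7.1% to 42.2% |
| 40% | 18 | 0.60 | 27.8% | 9.7% to 53.5% |
| 60% | 12 | 0.40 | 41.7% | 15.2% to 72.3% |

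**3. Zero events.** The exact two-sided 95% upper limit is 1 − 0.025^(1/n). For n = 30 it is 11.6%. For n = 24, 18 and 12 it is 14.2%, 18.5% and 26.5%.

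**4. Arm imbalance.** Let k be the number of phakic eyes in one arm when 18 of 30 are phakic; k is hypergeometric (30, 18, 15). The arms differ by 4 or more when |2k − 18| ≥ 4, that is k ≤ 7 or k ≥ 11, with probability 0.264. With 24 phakic eyes the corresponding probability is 0.169. To see the effect, suppose the same 30% at-risk rate in both arms and 12 against 8 eyes at risk. The expected all-subject rates are 0.30 × 12/15 = 24% and 0.30 × 8/15 = 16%, with no true difference.

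**5. Acuity.** Letters = 85 − 50 × log10(Snellen denominator/20). At 20/320 this gives 24.8 and at 20/250 it gives 30.2. Only eyes at the bottom of the admitted range are affected.

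**6. Which results are touched.** Every treated subject can have some ocular adverse event and some non-ocular adverse event. Steps 1 to 4 therefore apply to the rates of the named components and not to the overall incidences in sections 3.3.1 and 4.8.2a.

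**The case against.** The strongest reply is that section 4.8.2 names a data source and not a divisor. A table of cataract progression in phakic eyes would be consistent with it. This stands: a reader might infer that the plan commits itself to understated rates, but the text does not go that far. The understatement needs two conditions, that such eyes enrol and that 30 is used for these events. What remains is that nothing in either document rules out the diluted rate, and the choice should be made before the data are summarised.

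A reader might also infer that the primary result as a whole is diluted. It is not. The primary endpoint is overall incidence, for which all 30 subjects are at risk; the individual events are named only in the objective.

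Three narrower points also stand.

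- Section 2.1 pairs new PDR with neovascularization of the iris or angle: "cataract progression, vitreous hemorrhage, new PDR or neovascularization of the iris or angle". An eye with PDR at entry remains at risk of the second part. The documents also leave new PDR undefined, so its exclusion from risk assumes the plain meaning of a first occurrence.
- Fellow eyes may be treated, and ocular events are not limited to the study eye. If events are counted per subject, a phakic fellow eye keeps the subject at risk of cataract. The unit must be settled first.
- The image examples in Appendix D include eyes with PDR, but they illustrate a measurement technique and do not show who will be enrolled. The argument rests on the entry criteria alone.

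Finally, the study is a pilot. Section 3.4 states that it is not powered for differences in severe adverse events and cannot settle the incidence of rare ones. The intervals in step 2 overlap widely, and an all-subject rate is a valid description if labelled as such. That is why the at-risk rate belongs beside the all-subject rate and should not replace it.

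**Conclusion.** The point holds in conditional form. Eligibility admits study eyes that cannot show three events named in the primary objective, and neither document sets an at-risk denominator or a unit of analysis. If such eyes enrol and 30 is the divisor, those component rates are understated by the factor r/30, zero-event upper limits are too low, and arm comparisons of these events can move with chance imbalance at entry.

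The size cannot be derived from the documents. Over the assumed 20% to 60% pseudophakic eyes, the reported cataract rate would be 80% down to 40% of the at-risk rate; if every eye is at risk there is no bias. No comparable figure can be given for PDR. The acuity component is the weakest of the three, because it touches only the lowest entry scores and depends on the assumed letter scale. Overall ocular and non-ocular adverse event incidence are unaffected. This is a worthwhile and cheap improvement to the reporting of the named events, not a flaw in the primary endpoint.

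**What to change.** In section 4.8.2 and the SAP:

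- Set the study eye as the unit for these three events, and list fellow-eye events separately.
- Keep the all-subject rate, labelled as such. Beside it, report by arm the number at risk and the at-risk rate with an exact 95% interval for:
  - cataract progression, in eyes phakic at baseline;
  - new PDR, in eyes without PDR at baseline, with neovascularization of the iris or angle as a separate item over all study eyes;
  - loss of more than 30 letters, in eyes with at least 31 letters at Day 0.
- Keep all 30 subjects as the denominator for overall ocular and non-ocular adverse event incidence and for all other events.

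The cost is a few lines of text. Section 4.5.1 already schedules slit-lamp and fundus examination, ultra-widefield angiography and ETDRS acuity at screening, so no visit, procedure or change in sample size is needed. The drawback is that the at-risk rates for these events will be less precise and may be higher than the all-subject rates.

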#### a. Primary Endpoint

- Incidence and severity of ocular adverse events, as identified by eye examination (including visual acuity testing)
- Incidence and severity of other non-ocular adverse events, as identified by physical examination, subject reporting, and changes in vital signs

#### 4.8.3 Efficacy Analyses

#### a. Secondary Endpoints

- Mean change from baseline in best-corrected visual acuity by the number of letters read correctly at months 6 and 12.
- Mean absolute change from baseline central foveal thickness at months 6 and 12 as measured by SDOCT (defined as the average thickness within the central 1 mm subfield)
- Proportion of eyes that were anatomically "dry" by SDOCT at months 6 and 12.
- Proportion of eyes gaining greater than or equal to 15 letters of vision at months 6 and 12.
- Proportion of eyes losing greater than or equal to 15 letters of vision at months 6 and 12.
- Proportion eyes with 20/40 or better best-corrected visual acuity at months 6 and 12.
- Comparison of angiography leakage from baseline to months 3, 6, and 12.
- Comparison of peripheral nonperfusion from baseline to months 3, 6, and 12.
- Comparison of previous anatomic anti-VEGF response to month 3, month 6, and month 12 anatomic response.
- Comparison of previous functional anti-VEGF response to month 3, month 6 and month 12 functional response

٠

#### 4.8.4 Missing Data

Analyses of efficacy and safety will be based on available cases, without imputation for missing values.

#### 4.8.5 Interim Analyses

An interim analysis is planned at 6 months. Reports of adverse events from this study may be reviewed and summarized periodically while the study is ongoing to ensure the safety of subjects.

#### 4.9 DATA QUALITY ASSURANCE

Accurate, consistent, and reliable data will be ensured through the use of standard practices and procedures.

# 5. ASSESSMENT OF SAFETY

# **Specification of Safety Variables**

Safety assessments will consist of monitoring and reporting adverse events (AEs) and serious adverse events (SAEs) that are considered related to ranibizumab, all events of death, and any study specific issue of concern.

#### 5.1 ADVERSE EVENTS

An AE is any unfavorable and unintended sign, symptom, or disease temporally associated with the use of an investigational medicinal product (IMP) or other protocol-imposed intervention, regardless of attribution.

This includes the following:

- AEs not previously observed in the subject that emerge during the protocolspecified AE reporting period, including signs or symptoms associated with DME that were not present prior to the AE reporting period.
- Complications that occur as a result of protocol-mandated interventions (e.g., invasive procedures such as intravitreal injections).

If applicable, AEs that occur prior to assignment of study treatment associated with medication washout, no treatment run-in, or other protocol-mandated intervention.

Preexisting medical conditions (other than the condition being studied) judged by the investigator to have worsened in severity or frequency or changed in character during the protocol-specified AE reporting period.

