# 3.3 OUTCOME MEASURES

#### 3.3.1 Primary Outcome Measures

The primary outcome measures for safety and tolerability are the following:

- Incidence and severity of ocular adverse events, as identified by eye examination (including visual acuity testing)
- Incidence and severity of other non-ocular adverse events, as identified by physical examination, subject reporting, and changes in vital signs

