# c. Preexisting Medical Conditions

A preexisting medical condition is one that is present at the start of the study. Such conditions should be reported as medical and surgical history. A preexisting medical condition should be re-assessed throughout the trial and reported as an AE or SAE only if the frequency, severity, or character of the condition worsens during the study. When reporting such events, it is important to convey the concept that the preexisting condition has changed by including applicable descriptors (e.g., "more frequent headaches").

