# h. AEs of Special Interest (AESIs)

AEs of Special Interest are defined as a potential safety problem, identified as a result of safety monitoring of the Product.

The ranibizumab Events of Special Interest are:

- Endophthalmitis
- Intraocular inflammation (including vitritis and uveitis)
- Cataract (Traumatic)
- Increased IOP
- ATEs including stroke
- Retinal Pigment Epithelium Tear
- Retinal Detachment

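### Sections 2.1, 5.1 and 5.6.2c of the Protocol conflict on whether vision loss from DME is an adverse event, and no rule gives a count by arm of losses above 30 letters

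*Protocol*

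**What the plan says.** Three parts of the Protocol bear on this.

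- Section 2.1 describes the primary objective through a list of safety events that begins "worsened acuity >30 letters, retinal detachment, endophthalmitis, cataract progression, vitreous hemorrhage". It makes no exception by cause.
- Section 5.1 opens with a general definition: "An AE is any unfavorable and unintended sign, symptom, or disease temporally associated with the use of an investigational medicinal product", whatever the attribution. A list follows, introduced as inclusive. One item covers newly emerging events, "including signs or symptoms associated with DME that were not present prior to the AE reporting period". Another covers "Preexisting medical conditions (other than the condition being studied) judged by the investigator to have worsened in severity or frequency".
- Section 5.6.2, item c, treats any condition present when the study starts as pre-existing. It has such a condition "reported as an AE or SAE only if the frequency, severity, or character of the condition worsens during the study". DME is not excepted.

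The primary outcome in Section 3.3.1, repeated in 4.8.2a, is "Incidence and severity of ocular adverse events, as identified by eye examination (including visual acuity testing"), with a parallel item for non-ocular events. The SAP adds a chi-squared comparison of ophthalmic AE frequency at the 0.05 level. The trial is unmasked (Section 4.2), with 15 subjects per arm (Section 3.1).

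**The concern.** The inclusion criteria require foveal-involving DME at entry, so DME is pre-existing in every study eye. If the edema worsens and the eye loses more than 30 letters, one section points away from recording an AE, another points towards it, and the primary objective names the loss outright. The endpoint and the SAP test count AEs and do not carry the Section 2.1 list forward. Whether the loss is counted can therefore depend on which section the investigator applies, and that judgement is made with the arm known. At stake is whether the primary safety table reliably contains an event that the primary objective puts first.

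**Working it through.** **1. No planned figure to reproduce.** Section 4.8.1 states that the sample size has no formal calculation. The check is textual, with arithmetic only for scale.

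**2. One case under each rule.** Take a study eye with DME at entry whose edema worsens and which loses more than 30 letters.

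| Rule | Is the loss an AE? |
|---|---|
| 5.1, general definition | Yes on a plain reading: unfavorable, unintended, any attribution |
| 5.1, item on new events | Only if the sign or symptom was absent before; not for a deficit already present that deepens |
| 5.1, item on pre-existing conditions | Not covered, because DME is the condition being studied |
| 5.6.2c | Yes: DME was present at the start and has worsened |
| 2.1 | Yes: named, with no exception by cause |

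The rules disagree, and no section says which prevails.

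**3. Where else the loss would appear.**
- The lead sentence of Section 4.8.2 brings ocular examinations and measurements from all 30 subjects into the safety summary. It specifies no threshold and no table by arm.
- Sections 3.3.2 and 4.8.3 report the proportion losing 15 or more letters, as a secondary efficacy endpoint at months 6 and 12. A loss that recovers between those dates would not show, and losses above 30 letters are not separated.

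**4. The other ocular events in Section 2.1.** Vitreous hemorrhage, new PDR and iris or angle neovascularization are newly emerging events under 5.1. Cataract progression is worsening of a condition other than DME, so 5.1 counts it. The exception does not touch them.

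**5. Scale, with assumed counts.** The documents give no rate for this event.
- One eye counted or not: 1/15 = 6.7 percentage points in its arm; 1/30 = 3.3 points overall.
- Clopper-Pearson 95% intervals: 0/15 gives 0 to 21.8%, 1/15 gives 0.2 to 31.9%; 0/30 gives 0 to 11.6%, 1/30 gives 0.1 to 17.2%.
- Pearson chi-squared without continuity correction, χ² = N(ad − bc)²/(product of the four margins):
  - 4/15 vs 0/15: 30 × (4 × 15)²/(15 × 15 × 4 × 26) = 4.62, p = 0.032.
  - 3/15 vs 0/15: 30 × (3 × 15)²/(15 × 15 × 3 × 27) = 3.33, p = 0.068.
  - Fisher's exact test gives 0.10 and 0.22.
  - One reclassified eye can therefore cross 0.05 in the uncorrected chi-squared test.
- Chance of at least one such event among 30, 1 − (1 − p)³⁰: 26%, 45%, 79% and 96% for assumed true rates of 1%, 2%, 5% and 10%.

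**The case against.** The best defence is that Section 5.1 does not exclude the loss. Its general sentence covers any unfavorable sign, and the list only illustrates it, so matching no item does not put an event outside the definition. Section 2.1 itself presents the loss as an adverse event, and the endpoint says that ocular AEs are found by examinations that include acuity testing. This stands: the defect is a conflict, not a ban. It does not settle the matter, because an explicit exception invites use and nothing ranks the sections.

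It is also fair to say that vision loss would not vanish. The safety summary takes in ocular measurements, and the SAP compares efficacy endpoints between regimens. A difference in acuity between arms could be seen there, though not as a primary safety count above 30 letters.

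A reader might infer that most of the Section 2.1 list can drop out because the list of AEs of special interest omits several of its events and names cataract only as "Cataract (Traumatic"). The documents do not support that. Section 5.6.2i uses that list to set reporting times to the manufacturer, and nothing makes it a list for counting the endpoint. Step 4 shows that 5.1 covers the other ocular events.

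A reader might also infer that uncounted losses would gather in the treat-and-extend arm and mask a difference between regimens. Criteria B and C foresee recurrence of fluid in that arm, so the direction is conceivable. But no rate is given for either arm, and Criterion C already acts at a smaller loss.

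**Conclusion.** The conflict among Sections 2.1, 5.1 and 5.6.2c is real and reaches the primary endpoint, but its reach is narrow: DME-driven acuity loss above 30 letters in the study eye, where an investigator relies on the 5.1 exception. Such a loss may go uncounted; the documents do not show that it must or will. The effect is 6.7 points per eye within an arm and 3.3 points overall, assuming 15 per arm and that the eye has no other ocular AE. The significance example further assumes a per-subject comparison between arms by uncorrected chi-squared. Neither the sample size nor alpha changes. This is a modest weakness with an inexpensive remedy.

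**What to change.** Reconcile Sections 2.1, 5.1 and 5.6.2c, saying which governs worsening of DME. Then state in Sections 3.3.1 and 4.8.2a and in the SAP that acuity loss of more than 30 letters from Day 0 in the study eye, at any visit, is derived from the ETDRS record. It should be tabulated by arm as a primary safety event, whatever the attribution and whether or not an AE form was filed.

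The exception in 5.1 need not be deleted for lesser changes. Deleting it would make any worsening of DME an AE, including a thickness rise of the kind that Criterion B anticipates, and would move anatomic fluctuation into the safety endpoint, mainly in the treat-and-extend arm.

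Scheduled visits can be less frequent in the treat-and-extend arm, so an any-visit count gives the monthly arm more chances to detect a transient loss. The number of acuity assessments per arm should be shown beside it.

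The cost is wording and one extra table. ETDRS acuity is already recorded at every visit, so no procedure is added. The reported incidence of ocular events may be somewhat higher.
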